8. GENERAL SPECIFICATIONS FOR STATISTICAL ANALYSES

This section provides a general overview of the methods to analyze the study data. Specific analyses will be reported in the appropriate section 9.

The statistical analysis performed for this study will be both descriptive and inferential.

Statistical Analysis Plan

Continuous (quantitative) variables will be summarized using descriptive statistics including number of non-missing values, mean, standard deviation, median, minimum, and maximum. When needed, the use of other percentiles (e.g., 10%, 25%, 75% and 90%) will be specified in the relevant section. Selected continuous variables will also be described in classes (e.g., age, ECG parameters, etc.).

Frequencies and percentages will be displayed for categorical data.

In principle, percentages by categories will be based on the number of patients, by study phase (dose escalation and expansion), assigned schedule, enrollment dose level and overall, in the study population selected.

All inferential statistical analysis is made using two-sided tests at the $\alpha=0.05$ significance level, unless specifically stated otherwise.

For the time-to-event endpoints, the survival curve and the quartiles (25th percentile, median, 75th percentile) will be estimated using the Kaplan-Meier method [6] and will be reported along with the corresponding 95% Confidence intervals (CIs).

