If  $\geq 2/3$  or  $\geq 2/6$  patients experience DLTs in the first cycle of treatment, the MTD is considered to have been exceeded. At this point Sponsor and Investigators may request to evaluate three more patients at the previous dose level (if only 3 patients were previously treated at that prior dose) or to explore an intermediate dose level (not yet tested) in order to more precisely define the MTD. Evaluation of safety profile and exposure in patients treated in the study will guide the selection of the intermediate dose level.

The first two patients in each cohort should be treated with at least two weeks of delay between the first and the second patient. In absence of 1st cycle DLT in the first patient, the third patient can be enrolled at any time. In presence of 1st cycle DLT in the first patient, the third patient can be enrolled only after the second patient has completed the first cycle without DLT. In case a cohort needs to be expanded to more than three patients, the additional patients can be enrolled simultaneously.

If a patient fails to receive at least 70% of the treatment in the first cycle for reasons other than treatment-related toxicities, or if a patient is not assessed for DLTs, an additional patient must be enrolled at the same dose level. A patient may also be replaced if, under particular circumstances (e.g. due to noncompliance), the assessment of DLTs is not possible as judged jointly by the Investigators and the Sponsor.

For each dosing schedule, intra-patient dose escalation can be applied only for individual patients for whom the Investigator believes this is in the patient's best interest based on a risk/benefit evaluation and in agreement with the Sponsor. In this case, the patient should have already received 2-3 cycles of treatment at the assigned dose level with no relevant toxicities and the higher dose level applied should already be proven to be safe.

In backfill cohorts patients may be enrolled simultaneously.

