For Europe countries, up to 4 backfill cohorts of up to 10 patients each may enroll at doses and schedules no higher than RP2D or exposure equivalent and may include the following: 1) first cycle at reduced dose/exposure relative to RP2D to collect additional PK, matched PK/ECG for standard E14 update exposure/QTc, biomarkers, and anti-cancer activity followed by subsequent cycle up to RP2D or exposure equivalent; 2) food effect with first cycle no higher than RP2D or exposure equivalent followed by subsequent cycle with standard meal on day 1 of cycle 2 only. After day 1 of cycle 2, patients will continue treatment in fasting condition.

In Phase II, the following cohorts will be studied in parallel:

Cohort 1 (40 patients with a futility analysis at 10 patients): patients with AML FLT3 Internal Tandem Duplication (ITD) mutation as assessed by central laboratory, who have failed standard of care including venetoclax and gilteritinib based therapies. Dose and schedule will be within the defined exposure cap rule defined above. The enrollment in this cohort may be restricted to patients with specific prior lines/therapies and/or mutations, based on Sponsor decision.

Cohort 2 (40 patients with a futility analysis at 10 patients): patients with AML FLT3 Internal Tandem Duplication (ITD) mutation as assessed by central laboratory, who have failed standard of care. Dose and schedule will be within the defined exposure cap rule defined above. The cohort may be restricted to patients with specific prior lines/therapies and/or mutations, based on Sponsor decision.

The Sponsor will control the patient assignment to cohorts and may terminate any cohort in any phase at any time during the study based on safety, PK or strategic reasons.

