9.8. Safety Analyses

Unless otherwise indicated, all safety analyses will be performed in the treated patient population, while considering study part (phase I and phase II), assigned schedule and by dose level. All collected safety data (adverse events, laboratory assessments, vital signs, ECG, concomitant medications etc.) will be presented in patients data listings.

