9.8.1. Treatment-Emergent Adverse Events

Treatment-emergent adverse events (TEAEs) are those events whose onset date is posterior or equal to the start date of treatment, and the ones already present before first treatment administration but still ongoing on treatment and worsening in severity, and/or seriousness, and/or relationship with study treatment/procedure. All analyses that are further described in appendix TLGs Mock-ups and Algorithms, will be based on TEAEs.

AEs will be coded using Medical Dictionary for Regulatory Activities (MedDRA) and their severity will be graded according to the NCI Common Terminology Criteria for Adverse Events (CTCAE, version 5.0).

For each schedule, dose level cohort and overall, the incidence of AEs will be grouped by System Organ Class (SOC) and by preferred term (PT). Each patient will be counted once according to the worst grade reported throughout the whole treatment period for each SOC and/or for each preferred term. If clinically indicated, selected AEs will be presented by treatment cycle (Cycle 1 vs. Cycles > 1). In addition, serious AEs, AEs with severity grade ≥ 3 , and AEs with a relationship to study treatment, will be reported separately.

The AE listing and summary table including all TEAEs will be provided. Separate listings for AEs related to study treatment, serious AEs, AEs with severity Grade ≥ 3 , AEs leading to treatment discontinuation, AEs leading to dose reduction, dose omission and cycle delayed will be also provided. The following summary tables will be also created:

- All TEAEs
- AEs related to study treatment
- AESI

- The analysis of number of occurrences of non-serious AEs, serious AEs, serious related to study treatment AEs and serious AEs leading to death by SOC and preferred term will be performed only for regulatory purpose since these data have to be recorded in at end of the trial. These analyses will be only reported as appendix in the CSR.

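### AE tables put each patient's worst grade over all treatment under the enrollment dose level or cohort, so AEs first arising after a planned step-up or intra-patient escalation are reported at the lower dose

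*SAP*

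**What the plan says.** **Grouping.** SAP section 8 sets percentages, in principle, "by study phase (dose escalation and expansion), assigned schedule, enrollment dose level and overall". It presents itself as an overview and adds: "Specific analyses will be reported in the appropriate section 9". SAP 9.8 then calls for safety analyses "while considering study part (phase I and phase II), assigned schedule and by dose level", without saying whether the level is the one at enrollment or the one being taken. SAP 9.8.1 tabulates AE incidence by schedule, by dose-level cohort and overall.

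**Counting.** SAP 9.8.1: "Each patient will be counted once according to the worst grade reported throughout the whole treatment period for each SOC and/or for each preferred term". No visible text assigns an AE to the dose being taken at onset.

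**Dose increases after enrollment.** In one backfill option (SAP 4.1; Protocol section 1, Dose-Expansion and Backfill), cycle 1 is given below the RP2D to collect PK, ECG, biomarker data and "anti-cancer activity followed by subsequent cycle up to RP2D or exposure equivalent". Separately, Protocol section 1 (Dose-Escalation) states that "intra-patient dose escalation can be applied only for individual patients", after 2-3 cycles at the assigned level without relevant toxicity.

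**Splits by cycle.** For AEs, the cycle 1 versus later split is conditional: SAP 9.8.1 limits it to selected AEs when clinically indicated, and the protocol's Statistical Methods summary plans it where appropriate. For laboratory grades, SAP 9.8.4 plans the split without condition. Dose modifications go into listings (SAP 9.6).

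**The concern.** A patient can have a clean record at the enrolled dose, move up, and have the first severe AE at the higher dose. One lifetime worst-grade count under the enrollment level puts that AE in the lower-dose row. The higher-dose row receives neither the AE nor the time at risk. In the step-up backfill option this happens by design. After intra-patient escalation it is likely, because the patient was chosen for tolerating the lower dose.

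At stake is how toxicity by dose reads in the clinical study report and in publications, and possibly in the DSUR, which SAP section 2 names as a possible use. Clinical AEs are the exposed part. They include the neuromuscular AEs of special interest seen during escalation (Protocol 11.5.1.1.3), which get their own summary table in SAP 9.8.1 and which the laboratory cycle split does not cover.

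**Working it through.** The documents give no figure for this point, so there is nothing of theirs to reproduce. The check has three parts.

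**1. How many patients**

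- SAP 4.1: up to 4 backfill cohorts of up to 10, so 4 × 10 = 40. Of about 180 planned patients, 40/180 = 22%.
- Protocol version 9, section 1: up to 4 cohorts of up to 14, so 4 × 14 = 56, and 56/180 = 31%. SAP section 2 lists EU protocol version 8.0 as its basis.
- Both are ceilings. Cohorts may be food-effect cohorts with no planned increase. Patients escalated individually come on top; the documents give no number for them.

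**2. Size of the shift, on assumed risks**

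Let pL be the chance of a grade ≥3 AE while on the enrolled dose, pH the chance of a first one after the increase, and f the share of patients whose dose is raised. The rate shown at the enrollment level is

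shown = pL + (1 − pL) × f × pH.

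Attributed by dose at onset, it would be pL. All three inputs are assumptions. With pL = 10%:

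| pH | f = 1/6 | f = 1/3 | f = 1 (step-up backfill) |
|---|---|---|---|
| 10% | 11.5% | 13% | 19% |
| 20% | 13% | 16% | 28% |
| 30% | 14.5% | 19% | 37% |

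Worked cell: 0.10 + 0.90 × 1 × 0.20 = 0.28. Over pL from 5% to 15% and pH from 10% to 30%, the f = 1 results run from 14.5% to 40.5%.

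Not all of this is a dose effect. With pH = pL = 10% the row still shows 19%, because the later cycles add time at risk. At f = 1 the fair comparison for the dose effect is therefore 28% or 37% against 19%, a gap of 9 or 18 percentage points.

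In a 14-patient cohort with pL = 10% and pH = 20%, the expected number shown is 14 × 0.28 = 3.9, against 14 × 0.10 = 1.4 arising on the starting dose. The binomial chance of showing at least 3 patients is 16% at a rate of 10%, 51% at 19% and 80% at 28%.

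**3. Which decisions it can reach**

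- MTD: defined by first-cycle DLTs (Protocol 5.4). Intra-patient escalation comes after 2-3 cycles, so it cannot enter.
- Backfill: doses are set relative to the RP2D and no higher than it, so the RP2D is already identified.
- Final SAP tables: produced after the last patient's final visit (SAP section 5, closing text). Dose decisions come from ongoing review by the investigators and the sponsor.
- Remaining route: Protocol section 8 reviews safety from all cycles before escalating, and Protocol 5.4 includes safety among the RP2D considerations. Late toxicity after an individual escalation could enter there, but that review does not wait for the final tables, and individual dose changes are documented in the eCRF (Protocol 9.2.3).

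**The case against.** The strongest reply is that the enrollment-dose wording is only a default. SAP section 8 is qualified and defers to section 9, where 9.8 and 9.8.1 speak of dose level and dose-level cohort. A step-up backfill cohort could already have its own column; nothing visible says it is pooled with patients who stayed at the lower dose. Protocol 12.3.6 and parts of SAP section 9 are redacted, and the analysis conventions sit in a separate mock-ups and algorithms appendix. A dose-at-onset rule there cannot be excluded. This stands as a limit on the claim. But the only visible definition of the level is the one at enrollment, and a single worst-grade count over all treatment does not fit with splitting by dose at onset. An exception should be stated in the SAP.

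A reader might infer that the tables blur the evidence behind the RP2D and the exposure cap. The documents do not support that, for the reasons in part 3 of the working. Protocol section 1 also ties the exposure caps to safety trends, with reference to the Investigator's Brochure, not to these AE tables.

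A reader might also infer that the dose-toxicity gradient is always flattened. That is not shown. Dose reductions are allowed (Protocol 9.2.3.2), and an AE arising after a reduction is charged to the higher enrolled dose. The net direction is unknown.

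Two further replies hold in part. Laboratory grades already have a firm cycle split, so the point concerns AE tables. A cycle split would also isolate most post-increase AEs in the step-up backfill option, but for AEs it is not guaranteed.

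**Conclusion.** The point holds as a reporting defect in the AE tables, as far as the visible text goes. AEs first arising after a step-up or an intra-patient escalation are shown at the lower dose and are absent from the higher-dose row. The MTD is untouched and the bearing on RP2D selection is small.

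The reach is at most 40 to 56 backfill patients, fewer with food-effect cohorts, plus individual escalated patients. The illustrative percentages rest on assumed risks and on little loss of patients before the step-up; the documents supply no rates. The conclusion would fall if the redacted text or the separate appendix already assigns AEs to the dose at onset.

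**What to change.** In SAP 9.8 and 9.8.1, define dose level and then:

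- (a) Make the cycle 1 versus cycles >1 split mandatory for all AE tables by dose, with cycle 1 AEs by starting dose as the main dose-toxicity table.
- (b) Show step-up backfill patients as their own regimen column, not pooled with patients who stayed at the lower dose.
- (c) For patients whose dose level changed, up or down, add a supportive table of AEs by dose level at onset, with patient-cycles at that level as denominator. Treat a planned loading/maintenance regimen (Protocol 9.1.1), which changes dose within cycle 1, as one level. State how a cycle with an unplanned mid-cycle change is counted.
- Keep the enrollment-dose table.

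The cost is SAP text and programming. No new data are needed: dose modifications are documented in the eCRF (Protocol 9.2.3), each grade change is to be reported (Protocol 11.5.1.9), and the TEAE definition already uses onset dates.

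There are downsides. A patient can appear in more than one column of table (c). The later-dose columns hold patients who tolerated the earlier dose and may carry cumulative toxicity from it. A footnote should state this. It is also the reason to keep table (c) supportive and not let it replace the enrollment-dose table.

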8.1. Handling Missing Data

Unless otherwise specified in this SAP, all data will be evaluated as reported and no imputation of missing values will be done, with the exception of time related endpoints, as specified in section 9.7.2. Specific information for imputing missing data, where appropriate, will be also documented in the separate appendix Tables, Listing and Graphs (TLGs) Mock-ups and Algorithms.

8.2. Analysis Conventions

All collected data will be presented in listings. Data not subject to analyses according to this plan will not appear in any tables or graphics but will be included only in the data listings. Partial dates in principle will not be imputed except for date of birth. Only year of birth will be collected in the database and to estimate patient's age, December 31st will be used to replace the missing month and day, respectively.

Study day will be calculated in reference to the date of first study treatment. The study day will be displayed in all relevant data listings.

The baseline visit will correspond to the last assessment with non-missing result performed before initial study drug administration, unless otherwise indicated in the appendix TLGs Mock-ups and Algorithms.

All analysis conventions are detailed in the separate appendix TLGs Mock-ups and Algorithms.

8.3. Analysis Software

Data processing, data listings, tabulation of descriptive statistics, calculation of inferential statistics, and graphical representations will be performed using SAS® Software (release 9.4 or higher) for Windows, unless otherwise specified.

9. STATISTICAL ANALYSES

9.1. Patient Disposition

The number and percentages of patients who were enrolled, and eventually discontinued before start of treatment will be presented. Frequencies of patients who completed and discontinued treatment, categorized by primary reason for treatment discontinuation will be provided in each analysis set. The patients not meeting the eligibility criteria, and who are considered protocol violators as well as the ones failing to receive a complete first cycle will be identified and described

Statistical Analysis Plan

by individual data listing. Reason for patients' withdrawal from study will be also presented. The analyses will be presented for all patients, regardless of the diagnosis at study entry. Frequencies of patients excluded from the evaluable population for DLT analysis as defined in section 7 will be provided. Patients excluded from the evaluable patient population for efficacy analysis as defined in section 7, and reason for exclusion will be also provided.

9.2. Protocol Deviations

Protocol deviations will be assessed for all enrolled patients and will be classified as important and non-important based on MKIA-088-001 Protocol Deviations classification document. The patients not meeting the eligibility criteria, and who are considered protocol violators as well as patients excluded from efficacy analysis, will be identified, and described by individual data listings.

9.3. Demographics and Other Baseline Characteristics

Demographic and other baseline characteristics will be summarized by descriptive statistics. Both enrolled and treated patients' population will be considered.

Quantitative descriptive statistics (mean, standard deviation, median, min, max) for age, weight, body mass index (BMI), systolic and diastolic pressure, pulse, and height at study entry will be presented. Frequency tabulations for sex, female reproductive status, age group, race and ECOG performance status will be also presented.

Frequency tabulations for AML including FLT3 ITD, FLT3 D835, and FLT3 I836 mutation status, will be presented. For each cohort involved descriptive statistics of the time elapsed from date of diagnosis/date of relapse to the actual start of treatment will be provided.

Medical history other than AML/CMML disease and conditions existing at baseline will be coded by MedDRA preferred term (PT) and presented in listings.

Frequency tabulations for number of lines of prior leukemia therapies will be presented. In listings the duration of each therapy, as well as the time from relapse to start of treatment will be reported.

Demographic information, AML/CMML disease history, medical history, prior therapies for enrolled patients will be provided in listings.

9.4. Previous or Concomitant Medications/ Procedures

Concomitant medications and concomitant procedures will be descriptively analyzed in the treated patient population. Concomitant medications will be coded by World Health Organization Drug (WHO Drug) Global B3 dictionary. The frequency and percentage of all concomitant medications will be summarized and listed by preferred term. Patients will only be counted once within ATC and preferred term.

9.5. New Anticancer Therapies / Procedures

No other approved or investigational anticancer treatment will be permitted during the study period, including chemotherapy, immunotherapy, biological response modifiers, hormones. The specific use of hydroxyurea to contain hyperleukocytosis is allowed only during the first cycle of treatment, unless leukocytosis occurring after Cycle 1 is considered related to a differentiation syndrome.

Data related to new anticancer therapies along with best response and relapse/PD date will be reported for all treated patients in data listing.

9.6. Treatment Exposure and Compliance

Descriptive statistics for number of cycles with at least one dose treatment of any amount and treatment duration will be presented in summary tables considering treated patients. Administered

The dose administered and any type of dose modifications, if present, will be reported for all treated patients in data listings.

[REDACTED]

Statistical Analysis Plan

[REDACTED]

[REDACTED]

[REDACTED]

[REDACTED]

[REDACTED]

[REDACTED]

- [REDACTED]
- [REDACTED]

[REDACTED]

- [REDACTED]
- [REDACTED]
- [REDACTED]
- [REDACTED]
- [REDACTED]

[REDACTED]

Statistical Analysis Plan

[Redacted text block]

[Redacted text block]

[Redacted text block]

[Redacted text block]

[Redacted text block]

[Redacted]	[Redacted]	[Redacted]
[Redacted]	[Redacted]	[Redacted]
[Redacted]	[Redacted]	[Redacted]
[Redacted]		

[Redacted text block]

Statistical Analysis Plan

[Redacted content]

Statistical Analysis Plan

[Redacted]

[Redacted]	[Redacted]	[Redacted]
[Redacted]	[Redacted]	[Redacted]
[Redacted]	[Redacted]	[Redacted]
[Redacted]	[Redacted]	[Redacted]
[Redacted]	[Redacted]	[Redacted]

[Redacted]

[Redacted]

[Redacted]

[Redacted]	[Redacted]	[Redacted]
[Redacted]	[Redacted]	[Redacted]
[Redacted]	[Redacted]	[Redacted]

[Redacted]

Statistical Analysis Plan

[REDACTED]

[REDACTED]

[REDACTED]

[REDACTED]

[REDACTED]

9.8. Safety Analyses

Unless otherwise indicated, all safety analyses will be performed in the treated patient population, while considering study part (phase I and phase II), assigned schedule and by dose level. All collected safety data (adverse events, laboratory assessments, vital signs, ECG, concomitant medications etc.) will be presented in patients data listings.

9.8.1. Treatment-Emergent Adverse Events

Treatment-emergent adverse events (TEAEs) are those events whose onset date is posterior or equal to the start date of treatment, and the ones already present before first treatment administration but still ongoing on treatment and worsening in severity, and/or seriousness, and/or relationship with study treatment/procedure. All analyses that are further described in appendix TLGs Mock-ups and Algorithms, will be based on TEAEs.

AEs will be coded using Medical Dictionary for Regulatory Activities (MedDRA) and their severity will be graded according to the NCI Common Terminology Criteria for Adverse Events (CTCAE, version 5.0).

For each schedule, dose level cohort and overall, the incidence of AEs will be grouped by System Organ Class (SOC) and by preferred term (PT). Each patient will be counted once according to the worst grade reported throughout the whole treatment period for each SOC and/or for each preferred term. If clinically indicated, selected AEs will be presented by treatment cycle (Cycle 1 vs. Cycles > 1). In addition, serious AEs, AEs with severity grade ≥ 3 , and AEs with a relationship to study treatment, will be reported separately.

The AE listing and summary table including all TEAEs will be provided. Separate listings for AEs related to study treatment, serious AEs, AEs with severity Grade ≥ 3 , AEs leading to treatment discontinuation, AEs leading to dose reduction, dose omission and cycle delayed will be also provided. The following summary tables will be also created:

- All TEAEs
- AEs related to study treatment
- AESI

- The analysis of number of occurrences of non-serious AEs, serious AEs, serious related to study treatment AEs and serious AEs leading to death by SOC and preferred term will be performed only for regulatory purpose since these data have to be recorded in at end of the trial. These analyses will be only reported as appendix in the CSR.

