#### Statistical Methods

Descriptive statistics and patients' data listings will be used in the characterization of patients' disposition, demographic and baseline characteristics, treatment exposure and safety variables. Analyses by treatment cohort and dose schedule will be provided for treatment exposure and safety variables. Additional analyses will be performed by treatment period (ie cycle 1 vs. cycles >1), if appropriate, for adverse events, and selected hematological and biochemical tests. Adverse events, hematological and biochemical toxicity will be classified according to the NCI CTCAE (version 5.0). The MedDRA (Medical Dictionary for Regulatory Activities) dictionary (version 21.0) will be used to code the reported adverse events. The anti-tumor activity will be assessed by considering the objective tumor responses defined according to the ELN recommendations for the AML population [6, 7] whereas for CMML patients the tumor response evaluation will be made according to disease specific IWG criteria [56]. All efficacy data will be documented in individual patients' data listings. Untreated patients will be identified and described separately. For the Phase II portion of the trial a futility analysis will be performed for each cohort after at least 10 evaluable patients at the same dose level are observed for at least 3 cycles (ongoing enrollment up to 10 more treated patients may continue while analysis is being performed) such that if at least one responder (i.e. one CR or CRi) is observed then the full cohort may proceed. Time-matched, replicate ECGs and PK samples will be used to explore for concentration-corrected QT interval responses. Such analyses will be further described in a separate analysis plan. For further details see Section 12.3.

Therapeutic Area:	Oncology
Product:	NMS-03592088
Indication:	Acute Myeloid Leukemia (AML) and Chronic Myelomonocytic Leukemia (CMML)
Protocol Number:	MKIA-088-001
Title of Study:	A Phase I/II Study of NMS-03592088, a FLT3, KIT and CSF1R Inhibitor, in Patients with Relapsed or Refractory AML or CMML

**Interim Analysis****CCI**Safety analysis:

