### 9.2.2. Duration of Treatment

Patients may continue on study treatment until disease progression, unacceptable toxicity, investigator decision, withdrawal of consent by the patient or other discontinuation criteria detailed in Section 10 are met. Note: If patient is clinically stable and has observation of blasts reduction or suspected disease stabilization in the judgment of the investigator the investigator may continue dosing after an adverse event taking into account dose modification in section 9.2.3.

A participant patient is considered to have completed the study if he/she has completed all phases of the study including the last scheduled procedure as shown in the Schedule of Events in Section 1.

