3.2.2. Secondary Endpoints (Phase I and Phase II)

- Overall safety profile of NMS-03592088 characterized by type, frequency, severity (graded using the National Cancer Institute Common Terminology Criteria for Adverse Events [NCI CTCAE] Version 5.0), timing and relationship to study therapy of adverse events, and laboratory and ECG abnormalities;
- Plasma pharmacokinetic profile and corresponding parameters of NMS-03592088 and its metabolites NMS-03593860 and NMS-03603422;
- Renal clearance and fraction of NMS-03592088 and its metabolites NMS-03593860 and NMS-03603422 excreted in urine (only Phase I);
- Secondary efficacy endpoints include, as defined by the ELN recommendations [2,3] and disease specific International Working Group criteria [4] :
 - Best Response by category,
 - Overall Survival (OS),
 - Time to Response (TTR),
 - Duration of Response (DoR),
 - Event-Free Survival (EFS),
 - Relapse-free Survival (RFS),

and proportion of patients bridged to hemopoietic stem cell transplantation (HSCT).

For AML only (For US Phase I and EU in Phase II) as defined by the 2022 ELN recommendations [2]:

- Complete Remission (CR) Rate,
- Complete Remission and Complete Remission with Partial Hematologic Recovery (CR+CRh) Rate,
- Overall Response Rate (ORR: CRc + CRh + MLFS + PR)], where CRc= CR + CRi,

and rate of conversion from transfusion-dependence to transfusion independence.

[REDACTED]

[REDACTED]

[REDACTED]

[REDACTED]

[REDACTED]

[REDACTED]

Statistical Analysis Plan

- [REDACTED]
- [REDACTED]
- [REDACTED]

Phase II: will not start in the US until substantial amendment.

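### Adverse event tables by dose and schedule are crude counts over unequal treatment lengths; in the readable text the only adverse event split by period is conditional

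*SAP*

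**What the plan says.** **Counting rule.** SAP 9.8.1 groups adverse event incidence by schedule, by dose level cohort and overall. For each system organ class or preferred term, "Each patient will be counted once according to the worst grade reported throughout the whole treatment period".

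**Percentage base.** SAP 8 takes patients, not time on drug, as the denominator: "percentages by categories will be based on the number of patients, by study phase (dose escalation and expansion), assigned schedule, enrollment dose level and overall".

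**Treatment length.** Protocol 9.2.2 sets no fixed duration: "Patients may continue on study treatment until disease progression, unacceptable toxicity, investigator decision", among other reasons. Protocol 10 stops treatment in patients without at least a partial response after 9 cycles, so responders can stay longer. Under Protocol 11.5.1.4 adverse events are collected until 28 days after the last dose, or until a new anticancer therapy if that starts sooner. The window therefore lengthens with treatment.

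**Time-based views.** For adverse events the SAP says "If clinically indicated, selected AEs will be presented by treatment cycle", with Cycle 1 set against later cycles. The Statistical Methods part of the protocol summary is also conditional but is not limited to selected events: "Additional analyses will be performed by treatment period (ie cycle 1 vs. cycles >1), if appropriate, for adverse events". For laboratory grades, SAP 9.8.4 commits without condition to tables for Cycle 1, later cycles and any cycle. SAP 9.6 summarises number of cycles and treatment duration, and SAP 8.2 puts study day in the listings.

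**Endpoint.** The secondary safety endpoint in SAP 3.2.2 includes "timing and relationship to study therapy of adverse events".

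**The concern.** A proportion of patients ever affected rises with the time they are observed, unless all the risk comes early. Time on drug here depends on how long the leukemia is controlled and on tolerability. It will probably differ between low and active doses, between the two schedules, and between Phase II cohorts with different prior therapy.

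A crude table then mixes toxicity with duration. A dose that keeps patients on drug can look worse than it is, and one that patients leave early can look better. At stake is how the reported safety profile by dose, schedule and cohort will be read, including any informal comparison of the loading/maintenance regimen with earlier regimens. The readable text specifies no unconditional summary of adverse event timing that would let a reader separate the two.

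**Working it through.** The documents state no figure on this point, so there is none to reproduce. They also give no risk per cycle and no expected number of cycles by dose. The values below are assumptions, varied to show the range.

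**1. Constant risk, fixed stay.** With risk h per cycle and k cycles, the crude proportion is 1 − (1 − h)^k.

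| Risk per cycle | 2 cycles | 6 cycles | 9 cycles |
|---|---|---|---|
| 5% | 9.8% | 26.5% | 37.0% |
| 10% | 19.0% | 46.9% | 61.3% |
| 20% | 36.0% | 73.8% | 86.6% |

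At 8%: 1 − 0.92² = 15.4% and 1 − 0.92⁶ = 39.4%.

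**2. Constant risk, variable stay.** Let patients leave after each cycle with probability d = 1/(mean cycles). The crude proportion is h / [1 − (1 − h)(1 − d)].

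- h = 8%, mean 2: 0.08 / (1 − 0.92 × 0.5) = 0.08 / 0.54 = 14.8%.
- h = 8%, mean 6: 0.08 / (1 − 0.92 × 5/6) = 0.08 / 0.2333 = 34.3%.
- h = 5%: 9.5% against 24.0%.
- h = 10%: 18.2% against 40.0%.

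**3. Front-loaded risk.** Take 20% in Cycle 1 and r per cycle afterwards. The crude proportion after k cycles is 1 − 0.8 × (1 − r)^(k−1).

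- r = 2%: 1 − 0.8 × 0.98 = 21.6% after 2 cycles; 1 − 0.8 × 0.98⁵ = 27.7% after 6.
- r = 0: 20% at any length, so no distortion.

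**4. What this looks like in small groups.** The table gives exact binomial probabilities that one of two equal-sized groups shows at least two more affected patients than the other. Fourteen is the largest backfill cohort in the protocol; 3 and 6 are the escalation cohort sizes in SAP 4.1.

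| True crude incidence | Patients per group | Longer-treated group higher by 2 or more | Reverse |
|---|---|---|---|
| 14.8% vs 34.3% | 14 | 0.71 | 0.03 |
| 14.8% vs 34.3% | 6 | 0.41 | 0.03 |
| 14.8% vs 34.3% | 3 | 0.18 | 0.02 |
| 21.6% vs 27.7% | 14 | 0.39 | 0.15 |
| 20% vs 20% | 14 | 0.24 | 0.24 |

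The last row is the chance baseline against which the 0.71 should be read.

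**5. Effect of the remedy.** At a constant 10% per cycle with 2 against 6 cycles, first events per patient-cycle at risk are 0.100 in both groups, and Cycle 1 incidence is 10% in both. Either summary removes the false difference.

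**The case against.** **Some material cannot be read.** Protocol 12.3.6 (Safety Analyses) is redacted, SAP 9.8.2 is blacked out, and SAP 9.8.1 refers to a separate appendix of table mock-ups and algorithms. Any of these may hold time-to-onset or exposure-based tables. A reader might infer that the timing part of the endpoint is not delivered at all. The documents do not support that. Study day in listings, duration tables, firm laboratory tables by period and the conditional adverse event split all exist. What stands is that the readable text specifies no unconditional summary of adverse event timing. Listings and a separate duration table do not supply one.

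**Dose decisions in this trial.** A reader might also infer that these tables distort the choice of dose. The MTD rests on first-cycle dose-limiting toxicities, which share a common window. The RP2D is chosen on PK, anti-blast activity, biomarkers and safety, before Phase II opens. The SAP's final analyses run only after the last patient's final visit. This objection holds in full.

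**Size and direction.** Constant risk is not an obvious default, particularly for a regimen whose loading period falls in the first five days of Cycle 1. A toxic dose can itself shorten treatment, so it is not a general result that active doses are penalised. Both points stand, and they limit the claim to risk that continues after Cycle 1.

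**Descriptive choice.** The study is non-randomised and the readable SAP plans no formal comparison of adverse events between groups. Crude incidence beside treatment duration is a legitimate descriptive summary. That lowers the priority. It does not explain why laboratory grades receive a firm split by period and adverse events do not.

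**Conclusion.** The point holds as a low-cost improvement to descriptive safety reporting, not as a flaw in dose finding. The firm adverse event tables count patients over unequal, open-ended treatment periods, and in the readable text their only split by period is conditional.

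The size depends on assumptions. With continuing risk of 5% to 10% per cycle and mean stays of 2 against 6 cycles, crude incidence differs by about 15 to 22 percentage points at identical risk (24.0 − 9.5 = 14.5; 40.0 − 18.2 = 21.8). With the front-loaded pattern (20%, then 2% per cycle) and fixed stays of 2 against 6 cycles, the gap falls to about 6 points (27.7 − 21.6 = 6.1). It is zero if all risk falls in Cycle 1. In cohorts of 3 to 6, chance variation will often hide the effect. It matters more in the expansion, backfill, Phase II and pooled groups.

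**What to change.** In SAP 9.8.1:

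1. Make the table of Cycle 1 against later cycles unconditional, by schedule and dose level, for all treatment-emergent, grade 3 or higher, related and serious adverse events. SAP 9.8.4 already does this for laboratory grades.
2. For the larger groups (expansion, backfill, Phase II cohorts, pooled), add patients with a first event per 100 patient-cycles at risk for related grade 3 or higher events, serious events and AESIs. Add time to first AESI onset.
3. Keep the crude tables.
4. If the redacted sections or the mock-ups appendix already specify these summaries, a cross-reference from 9.8.1 is enough.

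The cost is a few extra tables from event dates and dosing records already collected, with no change to trial conduct. Rates per patient-cycle assume roughly constant risk, which the table by period helps to check. They are unstable in groups of 3 to 6, which is why item 2 is limited to the larger groups.
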